8.1.7 Abuse, Misuse, Overdose, and Medication Error

Abuse, misuse, overdose, or medication error (as defined below) must be reported to the sponsor according to the SAE reporting procedure whether or not they result in an AE/SAE as described in Section 8.2. Note: The 24-hour reporting requirement for SAEs does not apply to reports of abuse, misuse, overdose, or medication errors unless these result in an SAE.

The categories below are not mutually exclusive; the event can meet more than 1 category.

- **Abuse** Persistent or sporadic intentional intake of investigational product when used for a nonmedical purpose (eg, to alter one's state of consciousness or get high) in a manner that may be detrimental to the individual and/or society.
- **Misuse** Intentional use of investigational product other than as directed or indicated at any dose (Note: this includes a situation where the investigational product is not used as directed at the dose prescribed by the protocol).
- Overdose Intentional or unintentional intake of a dose of an investigational product exceeding a prespecified total daily dose of 1 capsule of the product.
- **Medication Error** An error made in prescribing, dispensing, administration, and/or use of an investigational product. For studies, medication errors are reportable to the sponsor only as defined below.

Cases of subjects missing doses of the investigational product are not considered reportable as medication errors.

Medication errors should be collected/reported for all products under investigation.

The dispensing, administration, and/or use of the unassigned treatment is/are always reportable as a medication error.

The administration and/or use of an expired investigational product should be considered as a reportable medication error.

All investigational product provided to pediatric subjects should be supervised by the parent/LAR/caregiver.

8.2 Serious Adverse Event Procedures

8.2.1 Reference Safety Information

The reference for safety information for this study is the SHP465 investigator's brochure which the sponsor has provided under separate cover to all investigators.

8.2.2 Reporting Procedures

All initial and follow-up SAE reports must be reported by the investigator to the Shire Pharmacovigilance Department and the CRO/Shire Medical Monitor within 24 hours of the first awareness of the event.

SHP465-309

07 September 2017

Note: The 24-hour reporting requirement for SAEs does not apply to reports of abuse, misuse, overdose, or medication errors (see Section 8.1.7) unless they result in an SAE.

The investigator must complete, sign, and date the Shire Clinical Trial Serious Adverse Event Form and verify the accuracy of the information recorded on the form with the corresponding source documents (Note: Source documents are not to be sent unless requested) and fax or e-mail the form to the Shire Pharmacovigilance Department. A copy of the Shire Clinical Trial Serious Adverse Event Form (and any applicable follow-up reports) must also be sent to the CRO/Shire Medical Monitor using the details specified in the emergency contact information section of the protocol.

8.2.3 Serious Adverse Event Definition

An **SAE** is any untoward medical occurrence (whether considered to be related to investigational product or not) that at any dose:

- Results in death.
- Is life-threatening. Note: The term 'life-threatening' in the definition of "serious" refers to an event in which the subject was at risk of death at the time of the event; it does not refer to an event which hypothetically might have caused death if it was more severe.
- Requires inpatient hospitalization or prolongation of existing hospitalization. Note: Hospitalizations, which are the result of elective or previously scheduled surgery for pre-existing conditions, which have not worsened after initiation of treatment, should not be classified as SAEs. For example, an admission for a previously scheduled ventral hernia repair would not be classified as an SAE; however, complication(s) resulting from a hospitalization for an elective or previously scheduled surgery that meet(s) serious criteria must be reported as SAE(s).
- Results in persistent or significant disability/incapacity.
- Is a congenital abnormality/birth defect.
- Is an important medical event. Note: Important medical events that may not result in death, be life-threatening, or require hospitalization may be considered an SAE when, based upon appropriate medical judgment, they may jeopardize the subject and may require medical or surgical intervention to prevent 1 of the outcomes listed in this definition. Examples of such medical events include allergic bronchospasm requiring intensive treatment in an emergency room or at home; blood dyscrasias or convulsions that do not result in inpatient hospitalization; or the development of drug dependency or drug abuse.

8.2.4 Serious Adverse Event Collection Time Frame

All SAEs (regardless of relationship to study) are collected from the time the subject signs the informed consent until the defined follow-up period stated in Section 7.1.3, and must be reported to the Shire Pharmacovigilance Department and the CRO/Shire Medical Monitor within 24 hours of the first awareness of the event.

In addition, any SAE(s) considered "related" to the investigational product and discovered by the investigator at any interval after the study has completed must be reported to the Shire Pharmacovigilance Department within 24 hours of the first awareness of the event.

8.2.5 Serious Adverse Event Onset and Resolution Dates

The onset date of the SAE is defined as the date the event meets serious criteria. The resolution date is the date the event no longer meets serious criteria, the date the symptoms resolve, or the event is considered chronic. In the case of hospitalizations, the hospital admission and discharge dates are considered the onset and resolution dates, respectively.

In addition, any signs or symptoms reported by the subject after signing the informed consent form, or leading up to the onset date of the SAE, or following the resolution date of the SAE, must be recorded as an AE, if appropriate.

8.2.6 Fatal Outcome

Any SAE that results in the subject's death (ie, the SAE was noted as the primary cause of death) must have fatal checked as an outcome with the date of death recorded as the resolution date. For all other events ongoing at the time of death that did not contribute to the subject's death, the outcome should be considered not resolved, without a resolution date recorded.

For any SAE that results in the subject's death or any ongoing events at the time of death, the action taken with the investigational product should be recorded as "dose not changed" or "not applicable" (if the subject never received investigational product).

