9.10 Safety Analyses

The safety data will be analyzed on the safety set. Safety endpoints include the occurrence of TEAEs, vital signs (systolic and diastolic blood pressure, pulse), BMI and weight, ECG results, clinical laboratory test results, and responses to CSHQ and C-SSRS.

Exposure to investigational product will be summarized.

Adverse events will be coded using the agreed upon version of the Medical Dictionary for Regulatory Activities. Treatment-emergent adverse events are defined as AEs that start or deteriorate on or after the date of the first dose of investigational product and no later than 3 days following the last dose of investigational product in the double-blind phase.

The number of events, incidence, and percentage of TEAEs will be calculated overall, by SOC, by preferred term, and by treatment group. Treatment-emergent adverse events will be further summarized by severity and relationship to investigational product. Adverse events related to investigational product, AEs leading to withdrawal, SAEs, and deaths will be similarly summarized/listed.

Vital signs (systolic and diastolic blood pressure, and pulse), weight, height, and BMI including potentially clinically important vital signs will be summarized by treatment and visit using the appropriate descriptive statistics.

The ECG results including potentially clinically important results will be summarized by treatment and visit.

Clinical laboratory test results will be descriptively presented by treatment group for each visit. Shifts of clinical laboratory abnormality from baseline to Visit 6/ET will be presented. Number and percent of subjects with potentially clinically important laboratory values will be presented by treatment group.

The PSQ results will be summarized by treatment and visit. Continuous variables, e.g., time to go to sleep and time spent awake, will be summarized using number of observations, mean and standard deviation, median, and minimum and maximum values. Categorical values, e.g., quality of sleep, will be summarized using number of observations and percentages. Detailed analyses of the PSQ will be described in the SAP.

The CSHQ results will be summarized by treatment and visit using appropriate descriptive statistics. Detailed analyses of the CSHQ will be described in the SAP.

The C-SSRS results will be summarized and listings of the C-SSRS data will be provided for subjects with a positive response.

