6. SUBJECT DISPOSITION

A listing of all Screen Failures (i.e., subjects who were screened but not randomized) will be presented along with reasons for screen fail and details of any adverse events (AEs).

The number of subjects included in each analysis set (i.e., Screened, Randomized, Safety, FAS) will be summarized by treatment group (SHP465 6.25 mg or Placebo) and overall, except for the Screened Set, which will be summarized only overall.

The number and percentage of subjects who completed and prematurely discontinued during the Treatment period will be presented for each treatment group and overall for the Safety Set. Reasons for premature discontinuation from the Treatment period, as recorded on the end of study discontinuation page of the electronic case report form (eCRF), will be summarized (number and percentage) by treatment group for the Safety Set. The subjects who completed the study are those that completed the final scheduled visit (Visit 6) at the end of the Treatment period.

In addition, the number and percentage of subjects who completed the study visits will be presented by visit for each treatment group and overall for the Safety Set.

All subjects who prematurely discontinued during the Treatment period will be listed by discontinuation reason for the Randomized Set.

Follow-up information, new (post-treatment) AEs and new (post-treatment) medication, will be listed for the Safety Set.

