12.1 Adverse Events

Adverse events will be coded using Version 18.0 of Medical Dictionary for Regulatory Activities (MedDRA).

An AE (classified by preferred term) that occurs during the Treatment period will be considered a TEAE if it has a start date on or after the first dose of double-blind investigational product or if it has a start date before the date of the first dose of double-blind investigational product, but increases in severity on or after the date of the first dose of double-blind investigational product. An AE that occurs after more than 3 days of the last dose of double-blind investigational product will not be counted as a TEAE. If more than 1 AE with the same preferred term is reported before the date of the first dose of double-blind investigational product, then the AE with the greatest severity will be used as the benchmark for comparison to the AEs occurring during the Treatment period under the preferred term.

An overall summary of the number of subjects with TEAEs in each treatment group will be presented, including the number and percentage of subjects with any TEAEs, serious TEAEs, TEAEs related to investigational product, TEAEs leading to drug withdrawal, severe TEAEs and serious TEAEs leading to death.

The number and percentage of subjects reporting TEAEs in each treatment group will be tabulated by system organ class (SOC) and preferred term; by SOC, preferred term, and severity; and by SOC, preferred term, and relationship to investigational product. If more than 1 AE occurs with the same preferred term for the same subject, then the subject will be counted only once for that preferred term using the most severe and most related occurrence for the summarization by severity and by relationship to investigational product.

The incidence of common (≥ 2% of subjects in any treatment group) will be summarized by preferred term and treatment group, sorted in decreasing frequency for subjects on SHP465 6.25 mg, and then for placebo. The incidence of TEAEs, serious TEAEs, and TEAEs leading to withdrawal will be summarized by SOC, preferred term and treatment group, sorted in decreasing frequency for subjects on SHP465 6.25 mg, and then for placebo.

For the Safety Set, listings will be presented for all AEs, TEAEs related to investigational product, TEAEs leading to drug withdrawal, and serious TEAEs.

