- Summary of duration of TEAE while on study drug: The duration of each event is the number of days from the onset of the TEAE, while on study drug during SHP465 6.25 mg, until the earlier of the end date of the TEAE or the date of last dosing + 3 days (if the date of last dosing is missing, the date of last day on study will be used). TEAEs that either overlap in time, or are adjacent in time will be merged into one TEAE only for the purposes of calculating duration of event. If a subject has multiple TEAEs that

Protocol SHP465-309

are not overlapping or adjacent in time, the durations will be averaged for that subject. Summary statistics are then based on the averaged subject durations. The calculated duration only includes the duration of TEAEs.

- Number and percentage of mild, moderate and severe TEAEs: Overlapping TEAEs with different preferred terms are counted as multiple TEAEs.
- Summary of the number of TEAEs per subject: Overlapping TEAEs with different preferred terms are counted as multiple TEAEs.
- Number and percentage of TEAEs that:
 - Resolved while on study drug
 - Ongoing
 - Dose interrupted
 - Dose withdrawn (and other action categories related to dose)
 - TEAEs leading to discontinuation
 - Number of subjects who discontinued investigational product due to the event

Also, for each of these 3 AEs, the following information will be presented by week:

- Number of subjects in the study
- Number and percentage of subjects with the TEAE
- Number of TEAEs
- Number and percentage of subjects who discontinued due to the TEAE
- Number and percentage of mild, moderate and severe TEAEs. If a subject has more than one TEAE in the same week, then the worst severity is counted.

Where, Week 1 includes TEAEs that start after Visit 2 (Baseline) through Visit 3 (Week 1), Week 2 includes TEAEs that start after Visit 3 (Week 1) through to Visit 4 (Week 2), Week 3 includes TEAEs that start after Visit 4 (Week 2) through to Visit 5 (Week 3), and Week 4 includes TEAEs that start after Visit 5 (Week 3) through to Visit 6 (Week 4).

In addition, for each subject, all occurrences of each of these 3 AEs will be listed separately by treatment group, subject, start date and stop date. The information presented will include: subject, sex, age, race, ethnicity, preferred term/adverse event, start date, stop date, onset day, study visit, last dose date, duration/imputed duration of TEAE (days), SAE, severity, effect on dosing and treatment for AE.

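### Protocol 8.2.6 asks for 'dose not changed' on any event that is fatal or ongoing at death, even where product had already been stopped because of that event

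*Protocol*

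**What the plan says.** Protocol 8.2.6 (Fatal Outcome) sets the recording rule. Its scope opens with "For any SAE that results in the subject's death" and extends to other events, fatal or not, that are unresolved when the subject dies: "any ongoing events at the time of death, the action taken with the investigational product should be recorded as 'dose not changed". The one alternative is "or 'not applicable' (if the subject never received investigational product".

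The outputs that might draw on that entry are these:

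- SAP 12.1 includes in its overall TEAE summary "TEAEs leading to drug withdrawal, severe TEAEs and serious TEAEs leading to death". It also tabulates TEAEs leading to withdrawal by system organ class and preferred term, and lists them.
- Protocol 9.10 states that "AEs leading to withdrawal, SAEs, and deaths will be similarly summarized/listed".
- SAP 12.1.1, for insomnia, weight decrease and decreased appetite only, counts events by "Dose withdrawn (and other action categories related to dose", with TEAEs leading to discontinuation on a separate line.

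Discontinuation also has its own record. Protocol 4.4 requires the reason for termination, the date product was stopped and the total taken to be in the source documents. Protocol 4.4.2 lists an adverse event among the reasons and has the most clinically relevant one entered on the CRF. SAP section 6 summarizes reasons "as recorded on the end of study discontinuation page of the electronic case report form".

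**The concern.** A dosed subject who dies has only one entry available for action taken, whatever happened to dosing beforehand. If product was stopped because of an event and the child later died with that event fatal or unresolved, the prescribed entry is untrue. The site would then hold an AE record showing no change in dosing beside a source record showing that dosing stopped, and why.

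The rule also pulls against two other duties. Protocol 8.2.2 has the investigator verify the SAE form against source, and protocol 9.1 has monitors compare the CRF with source and have discrepancies addressed. A site following 8.2.6 to the letter would create a mismatch that those sections ask it to resolve.

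At stake is the accuracy of the AE record for a small but important set of events and, depending on an unstated programming choice, whether those events are counted as having led to withdrawal. No efficacy result, power or error rate is touched.

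**Working it through.** The plan gives no figure on this point, so the check sets the sections side by side.

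**Step 1: can the situation arise?** Yes. Protocol 8.1 follows AEs to closure even after the subject leaves the study, so product can be stopped for an event and death can follow while the event is open. As an invented example, product is stopped on Day 10 because of an event and the child dies on Day 14.

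**Step 2: what would be recorded, and where would the event still appear?** Each case below assumes the event is a TEAE, meaning that it began or worsened between first dose and 3 days after last dose (SAP 12.1).

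| Case | Entry under 8.2.6 | True? | Other outputs that still show it |
|---|---|---|---|
| Fatal SAE, dosing unchanged up to death | dose not changed | Yes | Serious TEAEs; TEAEs leading to death |
| Fatal SAE, product stopped earlier because of it | dose not changed | No | Serious TEAEs; TEAEs leading to death |
| Serious non-fatal event that led to stopping, ongoing at death | dose not changed | No | Serious TEAEs |
| Non-serious event that led to stopping, ongoing at death | dose not changed | No | General TEAE tables only |
| Event that led to stopping, then changed severity before death | Earlier record is closed, so 8.2.6 does not reach it | Not affected | Earlier record keeps its own action entry |

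The fifth row follows from protocol 8.1.1, which captures a change in severity as a new event. Never-dosed subjects take the other entry and cannot have a TEAE, so that option does not help in any of the false cases.

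**Step 3: do the false entries reach the withdrawal tables?** Neither SAP 12.1 nor protocol 9.10 names the source variable. There are two possibilities:

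- *The tables use the action-taken field.* The events in rows two to four would be missing from the withdrawal outputs. The fourth row loses most, because neither the serious nor the death output shows it.
- *The tables use the discontinuation page or a separate flag.* The events stay in, but the AE record and the discontinuation record disagree and neither document says which governs.

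Some indirect evidence favours the first. Tabulation by preferred term needs withdrawal to be tied to a particular event, and nothing says that the discontinuation page identifies the responsible AE. On the other side, SAP 12.1.1 keeps the withdrawn-dose category and TEAEs leading to discontinuation on separate lines, which suggests that the two are not the same variable. The documents do not settle it.

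**Step 4: size.** About 60 subjects randomized 1:1 gives 60 / 2 = 30 per arm. If the first possibility holds and one child is affected, that arm's incidence reads 0/30 instead of 1/30, a difference of 3.3 percentage points. The documents give no expected death rate, so an expected number of affected events cannot be calculated.

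**The case against.** The strongest case on the other side is that the text supports only a recording inconsistency. Four parts of it stand.

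- A reader might infer that these events drop out of the withdrawal tables. The documents do not support that as a fact, because the source variable is unstated and 8.2.6 leaves the discontinuation page unchanged. The dose-action categories in SAP 12.1.1 serve three named AEs, not AEs in general.
- A reader might infer that sites are compelled to make a false entry. For action taken 8.2.6 says 'should', whereas for the fatal outcome it says 'must', and source verification gives a route to correction.
- A reader might infer that information on what followed stopping the drug is hidden from the safety report. The SAE form is not among the documents, so its content cannot be judged, and the stopping date is required in source.
- Other rules narrow the problem. Severity changes create separate records under 8.1.1, and 8.2.5 asks for signs and symptoms leading up to an SAE to be recorded as AEs where appropriate.

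What does not stand is any suggestion that the rule is harmless as written. None of these points makes the prescribed entry true when product had been stopped because of an event that kept the same severity until death. Source checking would expose the contradiction, but 8.2.6 would still direct the site to the wrong answer.

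**Conclusion.** The point holds in a limited form. For a dosed subject, 8.2.6 prescribes an entry that is false whenever product had been stopped or otherwise changed because of an event that proved fatal or was ongoing at death, and that entry conflicts with the record protocol 4.4 requires. That much rests on the text alone.

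The effect on the TEAEs leading to drug withdrawal is conditional on those outputs being derived from the action-taken field. If they are, the real loss is the non-serious event ongoing at death, since fatal TEAEs remain visible elsewhere.

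The practical impact is minor. It needs a death in about 60 children treated for 4 weeks, preceded by a change in dosing because of the event, and the 3.3-point figure describes one hypothetical child, not an expectation.

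**What to change.** Reword the last paragraph of protocol 8.2.6 so that the action actually taken with product before death is recorded. 'Dose not changed' would apply only when product had not been stopped or otherwise changed because of the event before death. 'Not applicable' would stay reserved for subjects never dosed. Align the CRF completion guidance.

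Add one line to SAP 12.1 naming the variable that defines a TEAE leading to drug withdrawal. This is needed in any case, because rewording 8.2.6 alone would leave the source of those tables unstated.

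The cost is one protocol sentence, the matching guidance and one SAP line, with no added data collection.
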